3.7 Baseline covariates definition

- Age (continuous)
Age as recorded at the time of consent, in years
- Site (categorical)
Five categories: UCLH, Sheffield, Bristol, Glasgow and Nottingham.

Baseline IIEF-5, ICIQ and IIEF-6 are defined above.

3.8 Subgroup definition

A subgroup analysis will be conducted according to the baseline pre-operative magnetic resonance imaging (MRI) recommendation for nerve sparing.

This will be defined as follow:

Bilateral nerve sparing recommended (BNSR) will be defined as having pre-operative nerve spare recommended on both the right AND on the left side by the MRI planning meeting.

Participants without BNSR (the main subgroup of interest) will be defined as those for whom nerve sparing was not recommended, or digital rectal examination (DRE) was recommended to guide the degree of nerve sparing, on either (or both) of the right and left sides. This would therefore include any of the following recommendations:

- (NS not recommended or DRE recommended) on the right side
- (NS not recommended or DRE recommended) on the left side
- (NS not recommended or DRE recommended) on both sides

Handling of partially missing information for BNSR

Participants with at least one of the side missing their NS recommendation will be considered as missing for BNSR.

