## 10.2 Multiparametric MRI prostate

All patients will have pre-biopsy mpMRI as per the local practice's diagnostic pathway. All radiologists will have at least 2 years of experience in prostate MRI reading. MRI diagnostic tumour detection performance is not formally assessed as all patients enrolling into NeuroSAFE PROOF already have tissue (biopsy) diagnosis of prostate adenocarcinoma and this is not the purpose of the trial. Radiologists are provided with clinical details including PSA, biopsy tumour results, biopsy method, medical history, and any other risk factors such as family history to aid their MRI interpretation. Local tumour staging (according to the PIRADS anatomic division of the prostate at the base, the mid gland and the apex) is graded according to a modified 5 level Likert scale based on the risk scoring system by the European Society of Urological Radiology (ESUR)(26), (1 = No signs of extra-prostatic extension (EPE), 2 = No convincing signs of EPE, 3 = EPE might be present, 4 = EPE is likely, 5 = EPE is highly likely).

Seminal vesicle invasion, lower sphincter invasion, and bladder neck invasion is reported as categorical ancillary reports. Subsequently, the radiologist using the mpMRI makes a NS recommendation for each side of the prostate for each participant regardless of treatment arm allocation. The radiological NS recommendation will be recorded:

- Nerve Sparing: Yes
- Nerve Sparing: No
- Digital rectal examination dependent.

Image-based mpMRI surgical NS planning is aimed to assist surgeons, but NS will still be performed in both control and intervention arm as per the operating surgeon's discretion.

During image based surgical NS planning, all mpMRI scans will be graded as to their quality according to the radiologist who reads the images. Scoring system will be a 1-5 Likert score. Description of criteria on scan required to give a quality score will be based on the following:

1. All three sequences are of insufficient quality to score any lesions.
2. Two out of the three sequences are not diagnostic; therefore, it is not possible to score any lesions.
3. It is possible to score a lesion (rule in) but it is not possible to exclude significant lesions (rule out).
4. One of the sequences is not of sufficient quality. Overall, it is possible to score the lesion (rule in) and rule out lesions in the background.

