4.10.2 Interaction test

We will assess whether the effect of NeuroSAFE on IIEF-5 at 12 months and ICIQ at 3 months differs according to pre-operative bilateral nerve sparing recommendation (BNSR), as defined in 3.9.2.

This will be assessed by testing for an interaction between BNSR and treatment arm in the primary and secondary outcome models (linear regression adjusted by site, age and baseline IIEF-5 or ICIQ).

Interaction test p-values will be interpreted in consideration of the low power of the interaction test, the number of subgroups tested, and the biological plausibility of the interaction.

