4.10.3 Subgroup analysis within the non-BNSR participants

We will compare outcome between the NeuroSAFE and standard arm, within the subgroup of participants where bilateral nerve sparing was not recommended.

We will estimate the difference in the primary (IIEF-5 at 12 month) and the main secondary (ICIQ at 3 months) outcomes between arms in this subgroup, using the same analysis model specified in section 4.7 and 4.8 (linear regression adjusted for age, site and baseline IIEF-5 or ICIQ) but restricted to participants without BNSR.

We may also report (without formal testing) on the difference in other secondary and descriptive outcomes within this subgroup, if appropriate.

Although this subgroup analysis may be less powered than the primary analysis of the trial, we expect around 2/3 of the trial participants to belong to this subgroup. This sample size should be sufficient power to detect moderate or large difference between arms.

We will not compare the outcomes within the converse subgroup (participants for whom bilateral never sparing was recommended), which would be of lesser relevance and likely to lack statistical power.

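### The SAP's missing-data rule for BNSR sets to missing men whom its own definition already places in the non-BNSR subgroup

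*SAP*

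**What the plan says.** SAP 3.8 builds the subgroup variable from two per-side MRI recommendations, each of which can be Yes, No or DRE-dependent.

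- **BNSR** means "having pre-operative nerve spare recommended on both the right AND on the left side by the MRI planning meeting".
- **Non-BNSR** means No or DRE "on either (or both) of the right and left sides". The list that follows names the right side, the left side, and both sides as qualifying patterns.
- **Missing data:** "Participants with at least one of the side missing their NS recommendation will be considered as missing for BNSR". The rule has no exception and no stated reason.

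Two analyses depend on this variable. The subgroup comparison in SAP 4.10.3 uses the main models, "but restricted to participants without BNSR". SAP 4.10.2 works by "testing for an interaction between BNSR and treatment arm in the primary and secondary outcome models". A man whose BNSR status is missing drops out of both. On size, SAP 4.10.3 says only that "we expect around 2/3 of the trial participants to belong to this subgroup".

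On data collection, Protocol 10.2 says the radiologist "makes a NS recommendation for each side of the prostate for each participant regardless of treatment arm allocation".

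**The concern.** The definition is an either-side rule, so one recorded No or DRE settles the class. The missing-data rule ignores this and requires both sides to be recorded. The same man is then non-BNSR under the definition and missing under the next rule.

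The SAP treats a comparable case differently. For surgical margins (3.6.6), a man is missing only when there is too little information to classify him.

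The non-BNSR men are the subgroup the SAP singles out, because it expects NeuroSAFE to help them most (3.8, 4.10.1). The SAP itself concedes that the subgroup analysis may have less power than the primary analysis (4.10.3) and that the interaction test has low power (4.10.2). Neither should lose men whose class is known. What is at stake is precision, and how well the analysed men represent the subgroup.

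**Working it through.** **1. The logic.** With Yes, No, DRE or blank on each side there are 4 × 4 = 16 patterns. In the 9 with both sides recorded, definition and rule agree (1 BNSR, 8 non-BNSR). In the 7 with a blank:

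| Pattern (either order) | Number of patterns | By the definition | By the missing-data rule |
|---|---|---|---|
| No / blank | 2 | non-BNSR with certainty | missing |
| DRE / blank | 2 | non-BNSR with certainty | missing |
| Yes / blank | 2 | undetermined | missing |
| blank / blank | 1 | undetermined | missing |

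Four of the seven are coded wrongly and three correctly. Reading a listed pattern as that side only does not change this. A man with No on the right and a blank left is then either right-only or both-sided, and both are non-BNSR.

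**2. The plan's own sample size.** SAP 1.4: 42% vs 28%, two-sided 5%, 80% power, 1:1. With pooled variance and no continuity correction:

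n per arm = [1.960 × √(2 × 0.35 × 0.65) + 0.842 × √(0.28 × 0.72 + 0.42 × 0.58)]² / 0.14² ≈ 181.0, rounded up to 182, so 364 in total.

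This matches the SAP. 364 / 0.90 = 404.4, against the stated 404. The SAP gives no count or power for the non-BNSR subgroup.

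**3. Subgroup size.** 364 × 2/3 ≈ 243 evaluable men.

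**4. Chance that a recorded side is No or DRE (q).** Assume both sides have the same q, and that 2/3 of men are non-BNSR:

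- findings never on both sides: 2q = 2/3, so q = 1/3
- sides independent: 1 − (1 − q)² = 2/3, so q = 0.423
- findings always on both sides: q = 2/3

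**5. Men regained.** Let m be the share of men with exactly one side blank. The documents do not give m, so it is assumed here, unrelated to the recommendation itself. Men regained = 364 × m × q.

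**6. Precision.** Subgroup n under the rule = 242.7 × (1 − m). After the fix, add the men regained. Detectable difference at 80% power, equal arms = 2 × (1.960 + 0.842) / √n, in SD units.

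| Assumed m | Men with one side blank | Regained (q = 1/3 to 2/3) | Detectable difference, current rule | Detectable difference, after fix |
|---|---|---|---|---|
| 2% | 7.3 | 2.4–4.9 | 0.363 SD | 0.360–0.362 SD |
| 5% | 18.2 | 6.1–12.1 | 0.369 SD | 0.360–0.364 SD |
| 10% | 36.4 | 12.1–24.3 | 0.379 SD | 0.360–0.369 SD |

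With no blank sides the detectable difference is 0.360 SD. With independent sides, the men regained number 3.1, 7.7 and 15.4.

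**The case against.** The logic is hard to contest, so the case against is about impact.

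- **No affected man is shown to exist.** The protocol plans a recommendation for each side for every participant. Protocol 10.1.1 describes a single planning sheet, so blanks may usually come in pairs (an inference), and paired blanks are rightly missing. SAP 2.4 also provides for missing values to be queried with sites. This stands: the number may be zero.
- **The gain is small.** At an assumed 5%, the detectable difference improves by less than 0.01 SD. This stands too.
- **The rule is explicit.** It sits under its own heading, and a programmer would know what to do. True, but a clear instruction can still give the wrong class. The SAP states no reason for the rule, which does not prove that there was none.
- **The repair is lopsided.** Once it is made, a man with one blank side can enter as non-BNSR but never as BNSR. This is correct and must be disclosed for the interaction test, which compares the two groups. The repair misclassifies no one.

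A reader might also infer that the current rule loses men selectively and so biases the comparison of arms. The documents do not support that. The rule drops every man with a blank side, whatever the recorded side says. The recommendation is pre-operative and is made regardless of allocation, and nothing indicates that blanks differ by arm.

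**Conclusion.** The point holds as an internal inconsistency in SAP 3.8. Men with No or DRE on one side and a blank on the other are certainly non-BNSR, yet they are removed from the subgroup analysis and the interaction test. That conclusion needs no assumption.

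The size does. For assumed one-side-blank rates of 2%, 5% and 10% of 364 men, and q from 1/3 to 2/3, about 2–5, 6–12 or 12–24 men out of about 243 would be regained. None of these rates comes from the documents, and the true number may be zero. The loss is one of precision and representativeness. The overall primary analysis does not use BNSR, so it and the 364/404 sample size are unaffected.

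It is still worth correcting, because the definition and the rule disagree about who belongs to the SAP's key subgroup and the repair uses data already collected.

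**What to change.** Narrow the rule in SAP 3.8 rather than delete it. Suggested wording:

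> If either recorded side is not recommended or DRE, the participant is non-BNSR. BNSR is missing only if no recorded side is not recommended or DRE and at least one side is missing.

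Add two statements:

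- Men with one side missing can enter only as non-BNSR.
- The interaction test will be repeated under the current rule (both sides recorded) as a sensitivity analysis.

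Reporting by arm how many men have one side blank, and what the recorded side says, would show whether the point matters in practice.

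The cost is a sentence or two in the SAP, one line of code and one extra model run. The change is best made before unblinding. Made later, it would be a post-hoc change to subgroup membership and should be labelled as such.

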3.9 Other descriptive variables

We list here briefly other relevant variables; the exact list and definition may be adapted at time of publication.

3.9.1 Baseline demographic characteristics

- Co-morbidities
 - Proportion of patients with any comorbidity (binary)
 - Proportion of patients with the four most frequent comorbidities (binaries)
- Ethnicity (categorical)
The ethnicity will be reclassified as White, Black, Asian and Other/Mixed.
- Body Mass Index (BMI, continuous)

Defined as weight(kg)/height(m)²

- Smoking status (categorical)

The smoking status classified as current smoker, ex-smoker, non-smoker and missing/unknown.

3.9.2 Baseline oncological characteristics and MRI

- Prostate volume (continuous)
- Baseline PSA (continuous)
- Histological classification
 - Gleason Grade Group (also known as International Society of Uropathologists (ISUP) grade group 1 to 5 (see table Appendix 7.4))
- Total cores (continuous)
- Positive cores

The percentage of positive cores is defined as percentage of positive cores = number of samples that were positive *100 / total number of samples taken during biopsy
- Maximum core length (continuous)
- Clinical T stage

Categorical: 1,2, or 3
- Cambridge prognostic group

Categorical: 1, 2, 3, 4 , 5.

See Appendix for detailed definitions.

3.9.3 Surgery procedure

- Overall surgical time (continuous)

Defined as the time from knife to skin to skin closed
- NeuroSAFE time (continuous)

Defined as the time between specimen removed for painting and decision phoned to surgeon)
- Lymph node dissection (Yes, No, Unknown)
- Nerve sparing outcomes
 1. By patient level (Bilateral vs Unilateral vs None)
 2. Quality of nerve spare on right (Grade 0, 1, 2, 3)
 3. Quality of nerve spare on left (Grade 0, 1, 2, 3)
- For NeuroSAFE arm only
 1. Negative NeuroSAFE

Defined as frozen sections R1 - R10 and L1 - L10 ALL equal to 'clear' or 'narrowly clear'
 2. Positive NeuroSAFE

Defined as ANY positive result in frozen sections (R1 - R10 and L1 - L10).
 3. Nerve bundles resected

Defined as patient taking right OR left bundle action

3.9.4 Pathology results

- Prostate weight (continuous)
- Histological classification

- Gleason Grade Group (also known as International Society of Uropathologists (ISUP) grade group 1 to 5 (see table Appendix 7.4))
- pT stage (Categorical)
 - Defined as pT2, pT3a, pT3b or pT4
- pN stage (Categorical)
 - Defined as pNx, pN0, or pN1
- Positive margins
 - See above for definitions
- Concordance to frozen section (NeuroSAFE arm only)
 - Frozen section concordant with final analysis of postero-lateral margin
- Presence of tumour in secondary resection (binary)
 - Cancer noted in the right or left secondary resection

4 Statistical analysis

4.1.1 Analysis populations

Intention-to-treat population (ITT) population: all participants who were enrolled in the trial and randomised.

Modified intention-to-treat (mITT) population: all participants who were randomised and received treatment (standard RARP or NeuroSAFE RARP)

Unless specified otherwise, analyses will be on mITT population

4.1.2 Handling of missing data

Frequency of missing data will be reported descriptively, as explained in section 4.6. We will explore baseline characteristics associated with missingness, using logistic regression on missing IIEF-5 at 12 months as outcome.

Handling of partially incomplete variables

In section 3.3 (Time points and dates), 3.4 and 3.5 (Outcomes), we explain how we will handle some of the partially missing observations. For example, if participants have responded at least 3 or the 5 IIEF-5 questions, we will replace the missing questions by 0 to obtain a conservative IIEF-5 score. These ad-hoc imputations when constructing the variables are all described in the outcome definition, in section 3

Handling of missing baseline covariates

For the outcomes adjusted analysis, if some of the baseline adjustment covariates (site, age, baseline IIEF-5, ICIQ or IIEF-6) are missing we will impute them using mean or mode imputation (White, 2005).

Missing outcomes

The main analysis (of the primary and secondary outcomes) will be based on all available data, under the missing-at-random assumption, i.e. that the probability of being missing is independent of the unobserved outcome, conditionally on the observed data in the model (arm and baseline covariates). Sensitivity analysis under different assumptions will be conducted, as described in 4.11.

4.1.3 Hypothesis testing

All statistical tests will be two-sided and considered significant at the 5% significance level, unless otherwise specified.

P-values reported will be for the null hypothesis of no difference between the two randomisation groups (NeuroSAFE RARP vs. standard RARP)

There is a limited number of tests conducted (one primary and three secondary outcomes, tested overall and within a subgroup), and no formal correction for multiple testing will be applied. The number of comparisons performed will be taken into account informally when interpreting the results.

Confidence interval reported will be at the 95% level, two-sided.

4.2 Participants flowchart

A flowchart will report the number of patients at each stage of the trial following the CONSORT guidelines.

The flow chart will report by arm: the number of participants randomised, receiving the surgery, completing visit 2, 3 and 4, and the reasons for early withdrawal from the trial.

4.3 Baseline characteristics

The baseline demographic and clinical characteristics (see list in section 3.9.1) will be summarised descriptively, overall and by randomisation arm, on the mITT sample. Mean, median, standard deviation, interquartile range, range (for continuous variables), or frequency and percentage (for categorical variables), will be reported as appropriate.

Baseline characteristics of participants who did not complete surgery will also be reported as additional information.

4.4 Surgery and pathology description

The surgery details and pathology results (see list of variables in sections 3.9.3 and 3.9.4) will be summarised descriptively by randomisation arm, on the mITT sample.

4.5 Adverse events

The number and proportion of participants who experienced any adverse events and any serious adverse events within 90 days from surgery will be reported by arm (frequency and proportion).

A table will describe the type of SAE experienced. We will also report how many were considered possibly related to the NeuroSAFE intervention.

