## 13.4 SAE Reporting

All serious adverse events (SAEs) must be reported to the NCITA Clinical Trials Unit within 24 hours of the Investigator's knowledge of the event (except for those that are identified in the protocol as not needing immediate reporting) via the appropriate SAE form. The trials unit will notify the main Research Ethics Committee and sponsor within 15 days of the Chief Investigator becoming aware of the event.

Those events arising will be reported on a three-monthly basis to the TMG and TSC/iDMC in a summary format, to include:

[figure not shown]
- The number of serious adverse events in a tabular format laying out the percentages of each type of serious events with an indication as to how many of those are thought to be related to the trial intervention.
- The total number of patients recruited during that same 3-month period and in total.
- Clavien-Dindo classified complications of 3 or more will be anonymised and blinded before being submitted to the TMG for central grading and review of site.

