## 13.5 Reporting Requirements

In line with the Health Research Authority guidance on non-CTIMP trials, only reports of SAEs that are listed below will require reporting to the CTU (and subsequently sponsor & ethics):

- **Related** to the trial (i.e. they resulted from the use of the NeuroSAFE technique) and
- **Unexpected** (that is not listed in section 13.7 – Expected Adverse Events)

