## 13.7 Expected Adverse Events

The following are expected adverse events following a radical prostatectomy with their corresponding likelihoods (31-34). These should be recorded in the patient's medical records but do not need an Adverse Event CRF to be submitted. These will be recognised as expected for trial treatment.

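### SAP 4.5 promises by-arm counts of any AE and any SAE to day 90, but protocol 13.7 requires no AE form for listed complications, and protocol 13.4 and 13.5 disagree on which SAEs reach the trials unit

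*SAP*

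**What the plan says.** **SAP 4.5** gives the harms output: counts and percentages of "participants who experienced any adverse events and any serious adverse events within 90 days from surgery will be reported by arm". It adds a table of SAE types and a count of those possibly related to NeuroSAFE. It does not name the form or database that supplies either row, and it does not say whether expected complications count.

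**SAP 3.1** schedules adverse events at Treatment and Visit 2. **Protocol 7.4** schedules them from screening to Visit 5. Neither schedule differs by arm.

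**Protocol 13.7** lists expected events with their likelihoods and says they go in the "medical records but do not need an Adverse Event CRF to be submitted". The list covers intra-operative, early post-operative and longer-term events.

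**Protocol 13.4** says that "All serious adverse events (SAEs) must be reported to the NCITA Clinical Trials Unit within 24 hours", "except for those that are identified in the protocol as not needing immediate reporting". It also requires a three-monthly SAE summary with "an indication as to how many of those are thought to be related to the trial intervention".

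**Protocol 13.5** says that "only reports of SAEs that are listed below will require reporting to the CTU". Two conditions follow: the SAE is related ("i.e. they resulted from the use of the NeuroSAFE technique") and unexpected ("that is not listed in section 13.7").

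**Protocol 13.7.1 and 13.7.2** require all deaths to be recorded and set the SAE observation period from consent to 90 days after surgery.

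**The concern.** A row labelled as any adverse event should rest on a rule that captures any adverse event. Here the protocol waives the form for the complications one most expects after prostatectomy. SAP 4.6 will report how often variables are missing, but a form that was never required does not appear as missing. A low count could be read as few complications when it reflects the waiver.

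The SAE row raises a different problem. Protocol 13.4 and 13.5 give different answers on which SAEs go to the trials unit. If a site followed 13.5 to the letter, SAE capture would depend on the arm, because a control patient never receives the NeuroSAFE technique.

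The table is descriptive and no primary or secondary result depends on it. It is, however, the by-arm harms report in this SAP.

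**Working it through.** The documents give no AE or SAE total to reproduce. The check is textual, with a sum for scale.

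**1. AE row.** The schedules place AE collection at Treatment and Visit 2, so AEs are collected in both arms over roughly the right period. They do not override the waiver in 13.7. A listed event therefore may or may not be entered, and SAP 4.5 does not say how it is then treated. The choice matters. Protocol 13.7 also lists temporary incontinence at 100% and erectile dysfunction at up to 100%. If every listed event counted, the row would be close to 100% in both arms. If none did, it would show only the unlisted remainder.

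**2. Scale.** The inputs are the likelihoods in protocol 13.7, per 100 men. The two near-universal longer-term items and the rest of that sub-list are left out.

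- Intra-operative: transfusion 1 + visceral injury 1 + vascular injury 1 + myocardial infarction 0.1 + atrial fibrillation 1.6 + syncope 1.2 = 5.9.
- Early post-operative: wound infection 2 + incisional hernia 2 + thromboembolism 0.8 + lymphoedema 1 + intensive care 2 + ileus or bowel damage 0.5 + seroma 1 + stricture 2 = 11.3.
- Total: 5.9 + 11.3 = 17.2 events per 100 men.
- With 202 men per arm (SAP 1.4): 17.2 × 2.02 = 34.7 events per arm.

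Some of these may reach the trial by another route or fall outside the window. Two assumptions are needed, and both are mine.

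- Serious items go by the SAE route. Narrowly, these are visceral injury 1, vascular injury 1, myocardial infarction 0.1, intensive care 2 and bowel 0.5, which sum to 4.6. Adding transfusion 1 and thromboembolism 0.8 gives a broad set of 6.4.
- Incisional hernia 2, lymphoedema 1 and stricture 2 all occur after day 90, which removes 5.0.

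Events with no required form, per 100 men and per 202-man arm:

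| Assumption | Per 100 | Per arm (× 2.02) |
|---|---|---|
| None removed | 17.2 | 34.7 |
| Narrow serious set removed | 17.2 − 4.6 = 12.6 | 25.5 |
| Broad serious set removed | 17.2 − 6.4 = 10.8 | 21.8 |
| Narrow set and late items removed | 17.2 − 4.6 − 5.0 = 7.6 | 15.4 |
| Broad set and late items removed | 17.2 − 6.4 − 5.0 = 5.8 | 11.7 |

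These are events, whereas SAP 4.5 counts participants. For the full 17.2, the share of men with at least one event is:

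- full overlap: the largest single rate, 2%, or 2 × 2.02 = 4 men per arm;
- independence: 1 − ∏(1 − p) = 15.9%, or 32 men per arm;
- no overlap: 17.2%, or 35 men per arm.

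**3. SAE row.** Under 13.5 as written, an SAE must satisfy both conditions.

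- A control-arm SAE cannot result from a technique the patient did not receive, so it fails the first. Only a death would still be recorded, through 13.7.1.
- A serious listed event, such as visceral injury needing laparotomy, fails the second in either arm. It then needs neither an AE form (13.7) nor a report to the unit (13.5).

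Several passages point towards wider capture.

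- Protocol 13.4 starts from all SAEs and exempts only immediate reporting.
- Protocol 13.4 and SAP 4.5 both count related SAEs as a subset, which would be pointless if every captured SAE were already related.
- Protocol 13.7.2 observes SAEs from consent. An SAE before surgery cannot result from the technique.
- Protocol 13.7.2 then says that deaths continue to be collected throughout, which implies that other SAEs are collected until day 90.
- The waiver in 13.7 names the AE form, not the separate SAE form.

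**The case against.** The strongest reply is that AEs are scheduled in both arms and that the literal reading of 13.5 is the weaker one. The second part stands. The passages listed above make it more likely that 13.5 was meant to limit only expedited onward reporting. Protocol 13.6, on the flow of SAE reporting, survives here only as an email line, and a flow chart there may settle the matter. But 13.5 places its limit at the trials-unit step and mentions sponsor and ethics only in parentheses, so the available text leaves the conflict open. The first part narrows the AE point without removing it, since the schedules do not cancel the waiver.

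It is also fair that counting every listed event would make the AE row uninformative, so leaving them out is defensible. In that case the row should say so.

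A reader might go further and infer that SAEs were recorded mainly in the NeuroSAFE arm, or that the harms comparison is biased between arms. The documents do not support this. The AE waiver applies equally to both arms, and nothing shows that sites followed 13.5 literally or that entry differed by arm.

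Finally, rewording the protocol recovers no event that went unrecorded, and the SAP describes data collection largely in the past tense. That is true, and it is why the SAP label matters more than the protocol wording.

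**Conclusion.** The point holds in a limited form. The AE row in SAP 4.5 is not assured to include the complications listed in protocol 13.7, and the planned missing-data report would not show the shortfall. The scale is at most about 35 events per 202-man arm without a required form, and about 12 if the broad serious set goes by the SAE route and the three late items all fall after day 90. The number of men is lower if events overlap.

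These figures assume that the 13.7 likelihoods apply in both arms, that the target of 202 per arm is met, and that sites entered no listed event voluntarily. The seriousness classification and the day-90 split are also assumptions.

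The SAE conflict between 13.4 and 13.5 is real on the face of the text. The better reading is that all SAEs to day 90 were meant to be captured. Only if 13.5 was followed literally would no control-arm SAE other than death be reportable. No between-arm difference is claimed for either row. Because the table is descriptive, this should be corrected but does not threaten the main results.

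**What to change.** 1. **Protocol 13.4 and 13.5.** Reconcile them. State explicitly that SAEs to day 90 are recorded in both arms whatever their relatedness or expectedness, and that 13.5 limits only expedited onward reporting. Confirm which rule sites actually followed.
2. **SAP 4.5.** Define the AE row as events recorded on a trial CRF and state that events listed in 13.7 were not required to be entered. Label the row *reported adverse events (incomplete capture of expected complications)* and draw no between-arm safety conclusion from it. Apply the same label to the SAE row if 13.5 was followed literally.
3. **Optional.** Add a by-arm table of Clavien-Dindo grade 3 or more complications from the central grading already described in protocol 13.4, after confirming that 13.5 did not filter that route.

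The cost is a protocol clarification, a few sentences in the SAP and a less favourable label. Expedited-reporting workload does not change.
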